Visit 2: 8 weeks after Visit 1 Day 1 (+2 weeks or up to +4 weeks in case of AEs which have not adequately recovered) subjects will receive the second administration of ¹⁷⁷Lu-OPS201 followed by safety and dosimetry evaluations over 8 days, with additional laboratory safety tests repeated at Day 15 (± 2 days). At 4 weeks (± 5 days) after Visit 2 Day 1 (Follow-up Visit 2), the safety of the subjects will be assessed. Additionally, subjects will receive a CT/MRI to monitor the RECIST v1.1 status and tumour volume changes.

Visit 3: 8 weeks after Visit 2 Day 1 (+2 weeks or up to +4 weeks in case of AEs which have not adequately recovered), subjects will receive the third administration of ¹⁷⁷Lu-OPS201 followed by safety and dosimetry evaluations over 8 days, with additional laboratory safety tests repeated at Day 15 (± 2 days). At 4 weeks (± 5 days) after Visit 3 Day 1 (Follow-up Visit 3), the safety of the subjects will be monitored.

EOCT Visit: 8 weeks (± 5 days) after Visit 3 Day 1, the safety and efficacy of the treatment will be evaluated. Subjects enrolled in Part A after the protocol version (v6.0) comes into effect will receive a CT/MRI scan to monitor the RECIST v1.1 status and tumour volume.

Part B

Visit 1: On Visit 1 Day 1, subjects will receive the first administration of ¹⁷⁷Lu-OPS201 followed by safety and extended dosimetry evaluations over 8 days, with additional laboratory safety tests repeated at Day 15 (±2 days). At Week 4 (Day 29±5 days), Week 6 (Day 42±5 days) (i.e. Follow-up Visit 1) and at the intermediate timepoints, the safety of the subjects will be assessed.

[figure not shown]
Visit 2: 8 weeks after Visit 1 Day 1 (+2 weeks or up to +4 weeks in case of AEs which have not adequately recovered) subjects will receive a CT/MRI scan to monitor the RECIST v1.1 status and tumour volume. Subjects will then receive the second administration of ¹⁷⁷Lu-OPS201 followed by safety and dosimetry evaluations over 8 days, with additional laboratory safety test repeated at Day 15 (±2 days). At Week 4 (Day 29±5 days) Week 6 (Day 42±5 days) (Follow-up Visit 2) and at intermediate timepoints, the safety of the subjects will be assessed.

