Evaluation of tumour change in volume from baseline to EOCT/EOAC/EW based on sstr2 positive lesions

Efficacy imaging endpoints will be assessed locally by the investigator up to the end of the 2-year long-term follow-up period and by the central imaging laboratory up to the EOCT/EOAC/EW Visit.

CCI

CCI

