1.3.2.2 Evaluation of Tumour Response

Tumour response will be evaluated by the site investigator and by an independent central review. The central review will be the data used for all imaging efficacy endpoints. Response and progression will be evaluated using the revised RECIST guideline (v1.1) and CCI [REDACTED]. Only subjects with measurable disease at baseline, who have received at least one cycle of therapy, and have had their disease re-evaluated will be considered evaluable for response.

All measurable lesions up to a maximum of two lesions per organ and five lesions in total, representative of all involved organs, should be identified as target lesions and recorded and measured at baseline. Target lesions should be selected on the basis of their size (lesions with the longest diameter), be representative of all involved organs, and permit reproducible repeated measurements. On occasion, if the largest lesion does not permit reproducible measurement, the next largest lesion which can be measured reproducibly will be selected. A sum of the diameters (longest for non-nodal lesions, short axis for nodal lesions) for all target lesions will be calculated and reported as the baseline sum diameters. If lymph nodes are included in the sum, then only the short axis will be added into the sum. The baseline sum of diameters will be used as reference to further characterise any objective tumour regression in the measurable dimension of the disease.

All other lesions (or sites of disease) including any measurable lesions over and above the five target lesions should be identified as nontarget lesions and should also be recorded at baseline. Measurements of these lesions are not required, but the presence, absence, or unequivocal progression of each should be noted throughout follow-up.

Overall objective tumour response will be classified as CR, PR, SD or PD, and unevaluable according to RECIST v1.1 at each visit. Based on objective tumour response, BOR, ORR, DoR and DCR will be calculated for both the central and the investigator review.

Time to PFS according to RECIST v1.1 will also be summarised.

Details of the response evaluation will be given in a separate image review charter.

CCI

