3.1.6 Secondary Efficacy Endpoints

The efficacy endpoints are:

- (a) Objective tumour response based on RECIST v1.1 (CT/MRI scan)
- Best overall response (BOR)

The best overall response according to RECIST v1.1 is defined as the best response recorded from the initiation of treatment until the EOCT/ EOAC/EW Visit, prior to the assessment of PD. Confirmation of complete or partial response is not required.

The following table provides a summary of the overall response status calculation at each time point for subjects who have measurable disease at baseline:

Table 4 Time point response

Target Lesions	Non-Target Lesions	New Lesions[a]	Time Point Response (TPR)
CR	CR	No	CR
CR	NCRNPD	No	PR
CR	NE	No	PR[b]
CR	NA[c]	No	CR
PR	NE	No	PR[b]
PR	CR	No	PR
PR	NCRNPD	No	PR
PR	NA[c]	No	PR
SD	NE	No	SD
SD	CR	No	SD
SD	NCRNPD	No	SD
SD	NA[c]	No	SD
NE	Non-PD	No	NE
PD	ANY	Yes/No	PD
ANY	PD	Yes/No	PD
ANY	ANY	Yes	PD

CR: Complete Response, PR: Partial Response, SD: Stable Disease, PD: Progressive Disease, NE: Not Evaluable, NCRNPD: Non-CR/Non-PD, NA: Not Applicable.

- a Identification of new lesions at a post-Screening time point will result in a TPR of PD. If an identified new lesion subsequently becomes NE, the TPR will be recorded as PD unless the new lesion has proven to have resolved. Note: TPRs assessed after a progression event will not contribute to the determination of the Best Response.
- b If a non-target lesion is classified as NE, a designation of PR may be assigned based on information from the target lesions.
- c No non-target lesions identified at Screening.

When SD or Non CR/Non Progressive Disease is believed to be the best overall response, it needs to be assessed a minimum of 8 weeks [56 days] after start of treatment. Otherwise, the best overall response will be NE, unless any Progressive Disease was further documented, in which case BOR will be Progressive Disease.

- Overall Response Rate (ORR)

The Overall Response Rate (ORR) is defined as the proportion of participants who achieved a Complete Response (CR) or a Partial Response (PR) as best overall response according to RECIST v1.1 criteria in the ITT Set. Subjects with no tumour assessment after the start of study treatment will not be evaluated.

- Disease Control Rate (DCR)

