The DCR is defined as the proportion of participants who achieved a Complete Response (CR), a Partial Response (PR) or a Stable Disease (SD) as best overall response according to RECIST v1.1 criteria in the ITT Set. Subjects with no tumour assessment after the start of study treatment will be considered as with no disease control.

- Sum of diameters as percentage change

- Percentage change from baseline in the target lesions identified in the RECIST v1.1 assessment and/or the initial lesion(s) identified at eligibility as being >20 mm in diameter, calculated as:

$$\text{Percentage change from baseline} = \frac{(D_i - D_0)}{D_0} \times 100$$

With

D_i the sum of the longest diameters of the target lesions as per RECIST v1.1 at the time point/Visit i .

D_0 the sum of the longest diameters of the target lesions as per RECIST v1.1 at baseline.

- Best percentage change from baseline in sum of target lesions longest diameters, calculated as:

$$\text{Best percentage change from baseline} = \frac{(D_{min} - D_0)}{D_0} \times 100$$

With:

D_{min} the minimum sum of the longest diameters as per RECIST v1.1 on all measurement time points.

D_0 the sum of the longest diameters of the target lesions as per RECIST v1.1 at baseline.

Correlations will be computed between dosimetry parameters (cumulative absorbed dose) and volume and diameter changes in lesions at the last visit of the core trial (EOCT or EACT or EW as applicable).

(b) Progression Free Survival (PFS)

PFS will be evaluated up to two years after the EOCT/EOAC Visit and will be based on RECIST v1.1 status assessed by investigator assessment. PFS will be assessed by independent central review up to EOCT/EOAC/EW Visit (during the core study part).

PFS is defined as the time from start of study treatment until occurrence of tumour progression or death.

(c) Quality of life using EORTC QLQ C30 v3.0 and QLQ GLNET21 (2006) questionnaires.

- EORTC QLQ C30 v3.0

The European Organisation for Research and Treatment of Cancer (EORTC) score questionnaire (QLQ-C30) will be used for quality of life (QoL) evaluation.

Following the EORTC recommendations, fifteen scales can be derived from the initial 30 questions:

- A global health status/QoL scale,
- Five functional scales (physical, role, cognitive, emotional and social),
- Nine “symptoms” scales /items (nausea and vomiting, pain, fatigue, dyspnoea, insomnia, appetite loss, constipation, diarrhoea and financial difficulties).

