3.2.3 Efficacy

All efficacy data will be included in the data listings and summary tables based on the ITT and PP sets. Summary tables will be presented by study part, cohort (part B only), overall part B and overall.

Tumour response will be evaluated by an independent central review and by the site investigator.. Response and progression will be evaluated using the revised RECIST guideline v1.1 and a modified RECIST (will be analysed for both Part A and B. The efficacy endpoint in the protocol only focus on Part B patients) guideline. Only subjects with measurable disease at baseline, who have received at least one cycle of therapy, and have had their disease re-evaluated will be considered evaluable for response.

Investigator assessment using RECISIT (V1.1) will be the primary assessment whereas central RECIST (V1.1) and mRECISIT (part B only) will be sensitivity analysis.

a) Overall Response, Best Overall Response and Overall Response Rate

Overall response at each visit will be tabulated and listed, as well as Best Overall response according to RECIST/CCI. Subjects with concurrent use of somatostatin analogues will be flagged in the listing.

For analysis of the ORR, summary tables will be generated, presenting the number and proportion of responders by study part, cohort (part B only) and overall on the ITT and PP sets, together with two-sided 95% Clopper-Pearson CIs. Subjects with no tumour assessment after the start of study treatment will be excluded from the analysis.

The same analysis might be repeated in the subsets of subjects with and without concurrent use of somatostatin analogues, if deemed relevant by the Sponsor.

The following SAS® code will be used for tables that need exact 95% Clopper-Pearson CIs:

```
PROC FREQ DATA=dset NOPRINT;  
    BY by var; (optional)  
    TABLES var1 /binomial (exact);  
    OUTPUT OUT=outname;  
RUN;
```

b) Disease control rate (DCR)

The number and proportion of subjects with disease control at end of either EOCT/EOAC (if independent central read) or end of long-term follow-up (if investigator) will be presented per study part, cohort (part B only) and overall on the ITT and PP sets, together with two-sided 95% Clopper-Pearson CIs. Subjects with no tumour assessment after the start of study treatment will be excluded from the analysis. The DCR will be based on the best overall response over all timepoints for independent central review and investigator assessment.

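### The SAP gives best overall response two windows: ORR and DoR stop at EOCT/EOAC/EW, although the primary investigator read, and DCR, run to the end of the 2-year follow-up.

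*SAP*

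**What the plan says.** **BOR and what depends on it.** SAP 3.1.6 defines BOR as the "best response recorded from the initiation of treatment until the EOCT/ EOAC/EW Visit", before any PD, with no split by reader. ORR is the share with this outcome: "achieved a Complete Response (CR) or a Partial Response (PR) as best overall response according to RECIST v1.1 criteria in the ITT Set". DCR is defined there on the same BOR; complete responders count, and so does "a Partial Response (PR) or a Stable Disease (SD) as best overall response according to RECIST v1.1 criteria in the ITT Set". SAP 3.2.3(g) restricts DoR to subjects whose BOR is CR or PR.

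**Readers.** SAP 3.2.3 names investigator RECIST v1.1 as the primary assessment and the central read as a sensitivity analysis. SAP 1.3.2 has imaging endpoints "assessed locally by the investigator up to the end of the 2-year long-term follow-up period", while central reading stops at EOCT/EOAC/EW. SAP 1.3.2.2 says something different: "The central review will be the data used for all imaging efficacy endpoints".

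**The second window.** SAP 3.2.3(b) states: "The DCR will be based on the best overall response over all timepoints for independent central review and investigator assessment". It takes the central DCR to EOCT/EOAC and the investigator DCR to the end of long-term follow-up. The waterfall plot in 3.2.3(c) sets BOR against best percentage change over the whole study. The ORR text in 3.2.3(a) gives no window of its own.

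**Part A scans.** SAP 1.2.1 and Protocol 3.1 schedule a scan at Follow-up Visit 2. For the EOCT visit they say: "Subjects enrolled in Part A after the protocol version (v6.0) comes into effect will receive a CT/MRI scan".

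**The concern.** The protocol describes GEP NETs as mostly slow-growing, and the final analysis waits for the end of the 2-year follow-up (Protocol 11.6). Yet under SAP 3.1.6 the primary investigator ORR cannot gain a responder after EOCT/EOAC/EW, which for three on-time cycles is 8 weeks after the last dose. A subject with SD at EOCT and a first PR in follow-up would be a non-responder for ORR, would have no DoR, and could appear in the waterfall plot with late shrinkage beside an SD label.

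A programmer who follows 3.1.6 and one who carries the reader-specific window of 3.2.3(b) across to ORR would produce different ORR and DoR tables from the same data, each with some support in the SAP.

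**Working it through.** No target, power or alpha is stated for BOR, ORR or DCR, so there is no planned figure to reproduce. The check compares windows and then counts scans.

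**1. Windows side by side (investigator read)**

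| Quantity | Source | Window closes at |
|---|---|---|
| BOR, hence ORR and DoR | SAP 3.1.6; 3.2.3(g) | EOCT/EOAC/EW |
| DCR, endpoint definition | SAP 3.1.6 | EOCT/EOAC/EW, through BOR |
| DCR, analysis text | SAP 3.2.3(b) | End of long-term follow-up |
| PFS | SAP 3.1.6(b) | 2 years after EOCT/EOAC |
| Best change in waterfall plot | SAP 3.2.3(c) | Whole study |

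PFS and the DCR analysis are split by reader. BOR is not, so the primary reader has a limit that fits only the central read.

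**2. Length of the window (on-time cycles)**

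- Three cycles: 24 of 24 + 104 = 128 weeks, or 19%.
- Five cycles: 40 of 40 + 104 = 144 weeks, or 28%.

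**3. Scheduled post-baseline scans**

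The inputs are the visit schedule at nominal weeks and eight follow-up visits (Protocol 5.2.9). For five cycles, EOCT and Visit 4 are taken as one visit.

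| Group | Scans in window (week) | Share of all scheduled |
|---|---|---|
| Part A with EOCT scan | 12, 24 | 2/(2+8) = 20% |
| Part B, three cycles | 8, 16, 24 | 3/(3+8) = 27% |
| Part B, five cycles | 8, 16, 24, 32, 40 | 5/(5+8) = 38% |
| Part A without EOCT scan | 12 | 1/(1+8) = 11% |

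The eight follow-up scans are a maximum, because scanning stops at progression.

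**4. Part A: is there an EOCT scan?**

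- Restricted to subjects enrolled after v6.0: SAP 1.2.1, the Protocol synopsis and Protocol 3.1.
- No such restriction: SAP Table 2, Protocol 5.2.8, Protocol 7.2.1 and SAP 1.3.2.1.
- Protocol 3.1 also says that the v6.0 imaging change affects only Part B.

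If the restriction applies, the only scheduled scan in the window falls 56 + 29 = Day 85 after on-time dosing (week 12), before Cycle 3 at week 16. The number of Part A subjects enrolled before v6.0 is not given; it lies between 0 and 15.

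**5. Effect on ORR of one late responder: 100/n**

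- n=6 (minimum Part A): 16.7 points
- n=15: 6.7 points
- n=40: 2.5 points
- n=55: 1.8 points

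Illustration with assumed counts, n=15, exact Clopper-Pearson limits: 2 responders give 13.3% (95% CI 1.7 to 40.5). One late responder more gives 3/15 = 20.0% (4.3 to 48.1), and three more give 5/15 = 33.3% (11.8 to 61.6).

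**6. Effect on DCR**

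A subject with SD as BOR by EOCT counts as disease control under either window. The windows differ only for a subject with no qualifying CR, PR or SD by EOCT/EOAC/EW who later has one without earlier PD.

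**The case against.** The best defence is that the EOCT limit may be deliberate. Other NET treatments are barred only until the end of the core study (Protocol 6.3.6), so later shrinkage may not belong to the study drug. Central reading also stops there, and a common cut-off keeps the two readers comparable. ORR is secondary and descriptive, and late shrinkage still appears in the response-by-visit tables and in best percentage change.

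Part of this stands. For the central read the limit is coherent, and no test or power claim is affected. For the investigator read the defence is weaker. The protocol puts no EOCT limit on tumour response (3.2.2.4), although it does on quality of life (3.2.2.5). SAP section 5 does not list the limit as a change from protocol. Later treatment can be handled by a cut-off at its start, as SAP Table 7 already does for PFS, and NET treatments are recorded during follow-up. SAP 3.2.3 still contradicts 3.1.6 whichever window was intended.

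Three stronger readings are tempting, but the documents do not support them:

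- **Early Part A subjects were judged on a single scan before Cycle 3.** This follows from the visit narrative but is contradicted by the schedule table and the procedure and imaging sections. An early-withdrawal scan or an unscheduled scan is also possible.
- **ORR is biased down by a known amount, or DCR is materially distorted.** The number of late responders is not given, and DCR is nearly insensitive to the choice of window.
- **Parts A and B cannot be compared because of scan timing alone.** They also differ in dose and lesion eligibility, and their scan schedules would stay unequal after the fix.

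**Conclusion.** The inconsistency is real and should be corrected, with moderate consequences. As written, SAP 3.1.6 leaves any first CR or PR seen after EOCT/EOAC/EW out of the primary investigator ORR and out of DoR, while SAP 3.2.3 uses the longer window for investigator DCR and for the waterfall plot's best change. Extending the window can only keep or raise the number of responders.

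The per-responder effects in the working assume full enrolment and that every subject has a post-baseline assessment, since ORR excludes those without one. The scan shares assume on-time visits and no progression during follow-up. The total shift cannot be estimated from the documents. The Part A point is conditional: one scheduled scan in the window if the v6.0 restriction applies, two if it does not.

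**What to change.** 1. In SAP 3.1.6, split BOR by reader, as PFS already is. Investigator BOR (for ORR, DCR and DoR) should use all evaluable scans from first dose to the first of PD, start of a new NET therapy, or end of long-term follow-up. Central BOR should close at EOCT/EOAC/EW.
2. Report the EOCT-limited investigator ORR as a supportive row.
3. Correct the SAP 1.3.2.2 sentence on central review so that it agrees with SAP 3.2.3, where the investigator read is primary.
4. Reconcile the passages on the Part A EOCT scan, and state how many Part A subjects were enrolled before v6.0.

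The cost is SAP wording and one table row; the follow-up scans are already scheduled and read locally. The downside is that late responses rest on local reads only, which the SAP already accepts for PFS and investigator DCR.

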2.1 Efficacy

2.1.1 Intent-To-Treat Set (ITT)

The Intent-to-Treat Set (ITT) consists of all subjects in the Eligible Subjects Set who received study medication.

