3.2.15 Rules and data formats

Data will be presented using an appropriate number of decimal places (i.e. the number of decimal places used does not imply undue precision). Raw data will be presented to the number of decimal places collected, and derived data will be presented to an appropriate number of decimal places. The appropriate number of decimal places will be determined by general practice, mathematical rationale or scientific rationale (e.g. age should be presented in whole numbers).

For summary statistics, the following will be presented n, number of missing values (based on subject who attended the visit), arithmetic mean, standard deviation, median and the range (minimum, maximum).

Mean, median, standard deviation and standard errors of the mean (SE) values will be reported to one decimal place greater than the raw/derived data that they summarise. Minimum and maximum values will be reported with the same precision as the raw data.

Percentages will be reported to one decimal place and 0% will not be presented. Percentages will be calculated using a denominator of non-missing observations. The denominator will be specified in a footnote to the tables for clarification if necessary.

Lower and upper confidence interval values will be presented to one decimal place more than the raw/derived data (i.e., to the same number of decimal places as the mean).

Percentiles (e.g., 25%, 75%) will be presented to one decimal place more than the raw/derived data.

If any, p-values will be reported to four decimal places (e.g.: p=0.0037), after rounding. P-values which are less than 0.0001 will be presented as '<0.0001'.

All values below or above a limit of detection (e.g. <0.1 or >100) will be listed as such.

All text fields must be left justified and numeric or numeric with some text specification (e.g.: not done, unknown, <4.5) must be decimal justified. Dates will be presented in the format [ddmmmyyyy] and times in the format [hh:mm].

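### The ORR labelled ITT leaves out treated subjects with no post-treatment scan, so it is a response-evaluable rate and cannot be lower than the ITT rate

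*SAP*

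**What the plan says.** SAP 3.1.6 defines ORR as the proportion achieving "Complete Response (CR) or a Partial Response (PR) as best overall response according to RECIST v1.1 criteria in the ITT Set". SAP 2.1.1 says that this set "consists of all subjects in the Eligible Subjects Set who received study medication"; it sets no condition about scans.

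The sentence after the ORR definition reads "Subjects with no tumour assessment after the start of study treatment will not be evaluated". Taken alone, that could mean only that such subjects receive no response category. SAP 3.2.3 a) settles it. It plans ORR by study part, "cohort (part B only) and overall on the ITT and PP sets, together with two-sided 95% Clopper-Pearson CIs", and then states "Subjects with no tumour assessment after the start of study treatment will be excluded from the analysis".

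Behind this stands an evaluability rule. Protocol 11.4.8, SAP 1.3.2.2 and the opening of SAP 3.2.3 all say that only subjects with measurable disease at baseline who received at least one cycle and "have had their disease re-evaluated will be considered evaluable for response". Neither document defines a response-evaluable analysis set. Protocol 11.4.3 and SAP 2.5 place efficacy on the ITT and PP sets.

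For the disease control rate (DCR) the SAP gives two rules. Section 3.1.6 says "Subjects with no tumour assessment after the start of study treatment will be considered as with no disease control", while 3.2.3 b) excludes the same subjects.

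**The concern.** A table headed ITT tells the reader that every eligible treated subject is in the denominator. Here that is true only if every one of them has a post-treatment tumour assessment. Any who do not are removed, and none of them could have counted as a response, so the reported rate cannot be lower than the ITT rate.

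Some routes out are plausibly related to poor outcome, death before the first scan most clearly. The study has no control arm in which the same omission might partly cancel. ORR is also to be shown by cohort, and six of the eight Part B cohorts enrol three to five subjects, where one missing subject changes the figure visibly.

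**Working it through.** **Who can drop out of the denominator.** The first scheduled post-treatment CT/MRI is at Visit 2 in Part B (about week 8) and at Follow-up Visit 2 in Part A (about week 12). A subject who stops treatment is due an Early Withdrawal (EW) Visit 8 weeks after the last dose (Protocol 4.6.1, 6.4.1, 6.4.2), and that visit includes CT/MRI (Protocol 5.2.10; SAP Tables 2 and 3). A subject stopping after Cycle 1 is thus due a scan at about week 8 in either part. Protocol 4.6.1 asks for the visit if possible, and Protocol 5.2.10 makes it depend on consent when a subject leaves the trial altogether. The subjects removed are therefore those who die before a first scan, decline the EW scan or are lost to follow-up. A scanned subject whose best response is not evaluable is not covered by the exclusion sentences and stays in as a non-responder.

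**Formula.** The documents state no expected or target ORR, so there is no planned figure to reproduce. Let n be the ITT subjects, m those never scanned after treatment and r the responders. All r are among the n-m scanned.

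- ITT rate: r/n
- Rate as the SAP computes it: r/(n-m)
- Ratio of the second to the first: n/(n-m)
- Difference: r·m / [n(n-m)]

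The two rates agree when m = 0 or r = 0; otherwise the SAP's rate is higher.

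**Numbers.** The documents do not give m, so every m below is an assumption. The sizes 55, 40 and 5 are the planned total, the planned Part B maximum and the upper size of a small cohort. For n = 55, r = 20 applies the 7/19 (37%) response in the earlier investigator study in Protocol 1.4. The other r values are illustrative. Intervals are exact 95% Clopper-Pearson, the SAP's method.

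| n | r | m | ITT rate r/n (95% CI) | As written r/(n-m) (95% CI) | Ratio | Difference |
|---|---|---|---|---|---|---|
| 40 | 10 | 4 | 10/40 = 25.0% (12.7-41.2) | 10/36 = 27.8% (14.2-45.2) | 1.111 | 2.8 points |
| 55 | 20 | 1 | 20/55 = 36.4% (23.8-50.4) | 20/54 = 37.0% (24.3-51.3) | 1.019 | 0.7 points |
| 55 | 20 | 6 | 20/55 = 36.4% (23.8-50.4) | 20/49 = 40.8% (27.0-55.8) | 1.122 | 4.5 points |
| 5 | 2 | 1 | 2/5 = 40.0% (5.3-85.3) | 2/4 = 50.0% (6.8-93.2) | 1.250 | 10.0 points |

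Check of the first row: 10 × 4 / (40 × 36) = 40/1440 = 0.028.

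**Consistency with DCR.** Take three subjects: one PR, one PD, one never scanned. ORR as written is 1/2 = 50%. DCR under SAP 3.1.6 is 1/3 = 33%, so response would exceed disease control, which is impossible on one population. Under SAP 3.2.3 b) DCR is also 1/2. The anomaly therefore arises only if the 3.1.6 DCR rule is the one applied, and the SAP does not say which is.

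**The case against.** The strongest reply is that the exclusion is prespecified and open. The evaluability rule is in the protocol and twice in the SAP, and the ORR sentences apply it. The SAP's general convention points the same way: "Percentages will be calculated using a denominator of non-missing observations". All efficacy data are listed, and SAP 3.2.5 plans a disposition table by population and assessment, so a reader could largely rebuild the full-ITT rate. This stands as a defence against any suggestion of concealment. It does not make the denominator the ITT Set, and no ORR table on the full set is planned.

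Second, few subjects may be affected. Eligibility requires a life expectancy of at least 6 months and a Karnofsky score of at least 60, and withdrawn subjects are due the EW scan. This also stands. A reader might infer that early withdrawals in general, including those for toxicity or clinical progression, leave the denominator. The documents do not support that, because a withdrawn subject who has the EW CT/MRI remains in.

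Third, a reader might infer that ORR and DCR are bound to have different denominators, or that an inflated ORR will be tested against an outside rate. Neither follows. SAP 3.2.3 b) gives DCR the same exclusion as ORR. The documents set no benchmark ORR and plan no formal test.

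Fourth, the shifts are small beside the intervals: 2.8 points against an interval of about 29 points in the 40-subject example. That is fair for precision, but the shift has a fixed direction and can be removed by wording alone.

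**Conclusion.** The point holds as a mismatch between the stated population and the denominator used. The rate labelled ITT is a response-evaluable rate, equal to the ITT rate multiplied by n/(n-m). The direction is certain whenever at least one eligible treated subject has no post-treatment assessment and there is at least one responder. The size is not known, because m is not given: under the assumptions above it runs from 0.7 to 4.5 points overall (one to six unscanned of 55), and is 10 points for one unscanned subject in a cohort of five.

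It would go too far to call this a demonstrated bias. If every treated subject is scanned, nothing changes. ORR is a secondary, descriptive endpoint, so no error rate is at stake. The change is still worth making, because it is cheap and the current label misstates what the table shows.

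**What to change.** 1. In SAP 3.1.6 and 3.2.3 a), state that in the ITT analysis of ORR, treated subjects with no post-treatment tumour assessment count as non-responders and remain in the denominator. Say that this overrides the non-missing denominator convention in SAP 3.2.15.
2. Report the response-evaluable ORR as a separately labelled supportive analysis, with the number excluded and the reasons (death before a scan, EW scan declined, lost to follow-up), by part and cohort.
3. State that the evaluability sentences in Protocol 11.4.8, SAP 1.3.2.2 and the opening of SAP 3.2.3 apply only to that supportive analysis. Without this step the new ORR rule would contradict them. Protocol 11 allows the SAP to modify planned analyses and asks for an amendment only for major changes to the primary endpoint or its analysis, so an entry in SAP 5 can record the change.
4. Use the same rule for DCR in SAP 3.1.6 and 3.2.3 b), which now disagree.

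The cost is a few SAP sentences and one supportive table. No new data are needed. The downside is a slightly lower headline ORR if any treated subject is never scanned.
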